9.3.1 Definition of primary endpoint(s)

The primary endpoint of the study is the ratio of the highest serum creatinine value up to and including Study Day 6 versus baseline.

9.3.2 Statistical model, hypothesis, and method of analysis

The log-transformed ratio of the highest serum creatinine value up to and including Study Day 6 vs baseline will be analyzed by a linear model, including log-transformed baseline serum creatinine value, treatment group, age and baseline eGFR as covariates. The estimated mean and 90% confidence interval of the difference in log-transformed ratios vs baseline between each TIN816 treatment group and placebo will be back-transformed to obtain the geometric mean ratio and corresponding 90% confidence interval, which will be reported along with the corresponding 1-sided p-value.

CCI

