Assessment to be recorded in the clinical database or received electronically from a vendor

S Assessment to be recorded in the source documentation only

¹ Visit structure given for internal programming purpose only.

² If the patient is in rehabilitation, this visit can be performed remotely

³ CCI

⁴ Check exclusion criterion # 11 (time on CPB pump) and #12 (active bleeding) before proceeding to study drug administration

⁵ CCI

⁶ CCI

⁷ Date of surgery, type of surgery, start/end time of surgical intervention, start/end time of cardio-pulmonary bypass, concomitant vasopressor medication and dose, any surgical re-assessment for bleeding

CCI [REDACTED]

⁹ Blood loss, urine output and fluid balance from beginning to end of surgery (before start of TIN816/placebo administration)

¹⁰ Vital signs will include the collection of body temperature (recorded in °C), blood pressure (BP) and pulse measurements.

¹¹ From collection bag if urine catheter still in place

¹² CCI [REDACTED].

¹³ This pre-surgery assessment can be performed on Day-1. If Screening assessment has been done on Day -1, no need to perform a new pre-surgery collection.

¹⁴ Only platelets count, leucocytes, erythrocyte count, hemoglobin, HCT need to be tested

¹⁵ To be performed only if clinically indicated to rule out active infection

¹⁶ CCI [REDACTED]

¹⁷ CCI [REDACTED]

¹⁸ CCI [REDACTED]

¹⁹ CCI [REDACTED]

²⁰ Time post TIN816/placebo infusion start; CCI [REDACTED]

²¹ CCI [REDACTED]

²² CCI [REDACTED]

²³ Duration of ICU stay, duration of overall hospital stay after cardiac surgery (from Day 1 to day of discharge), occurrence/date of any rehospitalization

2 Introduction

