4.2 Scientific rationale for study design

Table 4-1 Rationale for study design

Study Design Aspect	Rationale
Targeted study population	
The inclusion criteria for this study were chosen following current knowledge on clinical and demographic factors associated with AKI and with a goal to enroll patients at highest risk for developing AKI after cardiac surgery. According to literature, subjects undergoing complex surgeries with long CPB times and patients with pre-existing kidney disease and other comorbidities as well as older individuals in general have a higher risk to develop AKI after the surgery. CCI
 
(Delanaye et al 2019) CCI

Study Design Aspect	Rationale
Randomization (strata, allocation ratio)	
(Pottel et al 2017, CCI [REDACTED])
 
Randomization decreases the chance of imbalance of participant characteristics between groups, thereby facilitating an unbiased assessment of safety, tolerability and efficacy. In addition, randomization prevents selection bias.
 
CCI [REDACTED]

Blinding	
The study is participant- and investigator-blinded until final database lock (except where indicated in Section 6.3) to reduce potential bias in the assessment of readouts.

Study Design Aspect	Rationale
Duration of study periods	
The study follow-up duration is 90 days to allow for a meaningful assessment of the safety, tolerability and efficacy of TIN816 in AKI. The incidence and severity of AKI will be assessed through the first week after surgery and the MAKE criteria will be evaluated at Day 30 and 90.
 
CCI [REDACTED]

Treatment groups	
The control group is placebo on top of standard of care because there is no approved treatment for AKI

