8.3.4 Estimated glomerular filtration rate (eGFR)

The eGFR 2021 CKD EPI creatinine equation that estimates kidney function without a race variable should be used for eGFR calculations during this study. A taskforce of members from the National Kidney Foundation NKF and American Society of Nephrology ASN assessed the accuracy of a new eGFR equation that incorporates creatinine but omits race, and concluded the new equation to be more accurate. Immediate implementation in all US labs was recommended in November 2021.

$$eGFR = 142 \times \min(SCr / \kappa, 1)^\alpha \times \max(SCr / \kappa, 1)^{-1.200} \times 0.9938^{Age} \times 1.012 \text{ [if female]}$$

where: SCr is serum creatinine in mg/dL, κ is 0.7 for females and 0.9 for males, α is -0.241 for females and -0.302 for males, min indicates the minimum of SCr / κ or 1, and max indicates the maximum of SCr / κ or 1.

The equation does not require weight because the results are reported normalized to 1.73 m² body surface area, which is an accepted average adult surface area.

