### 2.3.2 Demographics and other baseline characteristics

Demographic and other baseline data including disease characteristics will be listed and summarized descriptively by treatment group for the safety analysis set.

Demographic table will include but not limited to the following information:

- Age
- Age group (45-64, 65-74, and  $\geq 75$ )
- For EU-CT requirement, Age group (18-64, 65-84, and  $\geq 85$ )
- CCI
- Sex
- Ethnicity
- Race
- Weight [kg]
- Height [cm]
- Body mass index (BMI) [kg/m^2]

The baseline characteristics table will include the following information:

- CCI
- 
- 
- 
- 
- Type of surgery (on Treatment Day 1)
- Duration of surgery (on Treatment Day 1) (Hours)
- Duration of Cardiopulmonary bypass (CPB) (Hours)

- Medical history with relevance to AKI (CKD, metabolic diseases, etc.)

Categorical data will be presented as frequencies and percentages. For continuous data, mean, standard deviation, median, minimum, and maximum will be presented.

Complete medical histories and current medical conditions at baseline will be summarized by system organ class and preferred term by treatment group using safety analysis set. A listing will be generated for medical histories and conditions.

A summary table for countries and sites by treatment group and overall will be created using the safety analysis set.

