### 2.5.2 Statistical hypothesis, model, and method of analysis

The log-transformed ratio of the highest serum creatinine value up to and including Study Day 6 vs baseline will be analyzed by a linear model, including log-transformed baseline serum creatinine value, treatment group, age and baseline calculated eGFR CCI as covariates. The estimated mean and 90% confidence interval of the difference in log-transformed ratios vs baseline between each TIN816 treatment group and placebo will be back-transformed to obtain the geometric mean ratio and corresponding 90% confidence interval, which will be reported along with the corresponding 1-sided p-value.

CCI

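### The stated primary model omits bypass duration and type of surgery, although the protocol names them as AKI risk factors and both are fixed before dosing; adding them is a cheap gain in efficiency and robustness.

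*Protocol*

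**What the plan says.** Protocol 9.3.1 defines the endpoint: "The primary endpoint of the study is the ratio of the highest serum creatinine value up to and including Study Day 6 versus baseline". Protocol 9.3.2 analyses its logarithm by a linear model "including log-transformed baseline serum creatinine value, treatment group, age and baseline eGFR as covariates". SAP 2.5.2 gives the same list, ending "treatment group, age and baseline calculated eGFR CCI as covariates", where CCI marks a redaction.

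On eGFR, Protocol 8.3.4 states: "The eGFR 2021 CKD EPI creatinine equation that estimates kidney function without a race variable should be used for eGFR calculations during this study". The equation takes creatinine, age and sex; of its sex-specific constants it says "κ is 0.7 for females and 0.9 for males, α is -0.241 for females and -0.302 for males".

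On surgical risk, the target-population row of Table 4-1 (Protocol 4.2) puts "subjects undergoing complex surgeries with long CPB times and patients with pre-existing kidney disease" at higher risk of AKI, along with other comorbidities and older age. Footnote 7 of the schedule of activities (Protocol 1.3) collects "type of surgery, start/end time of surgical intervention, start/end time of cardio-pulmonary bypass". SAP 2.3.2 lists type of surgery and CPB duration among the baseline characteristics to be tabulated.

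On timing, Protocol 1.1 randomises at the start of surgery on an expected CPB time of at least 60 minutes. It allows the infusion only after the actual time is confirmed to meet that limit. Protocol 9.3 runs the primary analysis on the PD analysis set, which contains treated participants only.

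**The concern.** The model adjusts for renal function and age, but not for the two surgical features that the protocol itself singles out. Whatever they explain of the post-operative creatinine rise stays in the residual variance. Each dose-versus-placebo interval may then be wider than the collected data allow, and a chance difference in surgical case-mix between groups goes uncorrected.

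The design gives a second reason. The two dose groups are enrolled one after the other, under different protocol versions (Protocol 4.1), and SAP 2.1 pools all placebo participants. Each dose is therefore compared partly with placebo participants from the other enrolment period. Randomisation does not balance case-mix across periods, and the stated covariates say nothing about surgical complexity.

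**Working it through.** **Inputs.** From the documents: N about 120 and three groups (Protocol 4.1); the covariate list (Protocol 9.3.2); the eGFR equation (Protocol 8.3.4); one-sided tests at 0.1 (Protocol 9.2.1). Redacted: allocation ratio, strata, planned power, effect size and SD, so the sample size cannot be reproduced. Not given: the partial R² (r) of CPB duration and surgery type for the log creatinine ratio. I take r from 0 to 0.15 as an assumption.

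**Step 1: can the covariates be used?** CPB duration becomes known after randomisation but before the blinded infusion, and it must be confirmed before dosing. Treatment cannot affect it, and it should be available for everyone in the analysis set. Type of surgery is likewise settled before dosing.

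**Step 2: what does eGFR add?** The equation was applied to simulated populations (assumed: mean age about 69, SD 9; 20 to 35% women; median creatinine in men 1.0 to 1.5 mg/dL; SD of log creatinine 0.25 to 0.35). Log creatinine and age explain 79 to 89% of the variance of eGFR, and 96 to 97% once sex is added. Restricted to eGFR below 60, log creatinine and age explain about 68%. So eGFR mainly brings in sex, which is not otherwise in the stated list, plus some curvature.

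**Step 3: cost of a covariate.** With g groups and q covariates balanced by randomisation, the expected variance of a treatment contrast is the residual variance × (1/n₁ + 1/n₀) × (N − g − 1)/(N − g − q − 1). This is exact for normal covariates and close otherwise. With N = 120 and g = 3 the last denominator is 116 − q:

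- without eGFR, q = 2: 114
- planned, q = 3: 113
- eGFR replaced by log CPB duration and binary surgery type, q = 4: 112
- both added to the planned model, or eGFR replaced by both plus sex, q = 5: 111

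The cost of keeping eGFR is √(114/113) − 1 = 0.44% of the SE. Simulation gave 0.4 to 0.5%.

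**Step 4: net change in SE.** The SE factor against the planned model is √[(1 − r) × 113/112] for replacing eGFR and √[(1 − r) × 113/111] for adding. This takes eGFR to have no prognostic value of its own.

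| r (assumed) | Replace eGFR | Add both, or replace eGFR and include sex |
|---|---|---|
| 0 | +0.45% | +0.90% |
| 0.02 | −0.56% | −0.12% |
| 0.05 | −2.10% | −1.66% |
| 0.10 | −4.71% | −4.28% |
| 0.15 | −7.39% | −6.98% |

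Simulated three-group trials (splits 40/40/40 and 20/60/40, assumed) agree to within about 0.1 percentage points. Break-even is r = 1 − 112/113 = 0.009 for replacing and 1 − 111/113 = 0.018 for adding. A three-level surgery type added to the planned model (q = 6) moves break-even to 1 − 110/113 = 0.027 and costs √(113/110) − 1 = 1.4% at r = 0. That favours a binary coding.

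**Step 5: in participants and power (adding both).** Equivalent N is 120/[(1 − r) × 113/111]: 118 at r = 0, 124 at 0.05, 131 at 0.10 and 139 at 0.15. If planned power were 80% (assumed), new power is Φ[(1.2816 + 0.8416)/factor − 1.2816]: about 79%, 81%, 83% and 84%.

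**The case against.** **Redactions.** Text is removed inside the SAP covariate list, after the model paragraph in both documents, in the randomisation details and in SAP 2.5.6, 2.5.7 and 4. Adjustment for surgery, or a supportive analysis with it, may be there. This stands as a limit on certainty. It does not remove the point: the protocol's covariate sentence is complete and lacks both factors. In the SAP the redaction follows eGFR, the last item after the conjunction, so it most naturally qualifies eGFR.

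**Prognostic strength is inferred.** Table 4-1 speaks of AKI risk, not of the log peak-creatinine ratio. Participants with CPB below 60 minutes are not dosed, which narrows the range of CPB duration. Renal function and age, named in the same sentence, are already adjusted for. All this stands and is why r must start at 0. It does not defeat the proposal, because the loss at r = 0 is below 1%.

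**eGFR as the fault.** A reader might infer that eGFR's collinearity with creatinine and age widens the treatment interval. It does not: in a randomised comparison, overlap among covariates affects their own coefficients, not the treatment contrast beyond one degree of freedom. Dropping eGFR without adding sex can even lose precision. If sex explained 3% of the outcome variance (assumed), the SE would widen by about 0.6%.

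**Late changes.** Protocol 6.3.2 lets the sponsor team see unblinded individual data at interim analyses. Changing the primary model after such a look would invite data-driven choice. This stands and governs the timing of the fix.

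**Conclusion.** The point holds as an efficiency and robustness improvement. The stated primary model leaves out two pre-dose factors that the protocol itself calls risk factors and already collects. Adding them costs at most about 1% of the SE if they carry no information, breaks even at a partial R² below 0.02, and saves about 4% at 0.10 and 7% at 0.15. These figures rest on N = 120, an assumed range for the partial R², and eGFR having no further prognostic value.

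Correcting chance imbalance is this same SE gain seen in a single trial, not an extra benefit. Help against drift in case-mix between the dose cohorts is separate. It reaches only what these two variables measure and cannot be sized, because allocation by period is redacted.

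Two stronger readings are not supported. The documents do not show the planned model to be wrong or biased: it is pre-specified and valid without these covariates. Nor do they show that precision is certainly lost, since no partial R² is given and relevant text is redacted.

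**What to change.** Unless the redacted text already does so, amend SAP 2.5.2 to add log CPB duration (minutes) and a binary type of surgery (for example isolated versus combined, with the coding rule stated). Keep treatment group, log baseline creatinine, age and any randomisation strata. Baseline eGFR may stay or be replaced by sex; if it is dropped, enter sex.

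Make the change before anyone who chooses the covariates has seen unblinded efficacy data, and in any case before database lock. If such a look has already taken place, leave the primary model as it is and specify the adjusted model as a supportive analysis.

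The cost is one or two sentences in the SAP and, on balance, one or two degrees of freedom. No new data are needed.

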9.3.3 Handling of intercurrent events of primary estimand

CCI

9.3.4 Handling of missing values not related to intercurrent event

CCI

9.3.5 Sensitivity analyses

Not Applicable

9.3.6 Supplementary analysis

Not Applicable

9.4 Secondary endpoint(s)/estimand(s) analysis

The secondary objectives of the study are provided in [Table 3-1](#).

9.4.1 Safety endpoints

For all safety analyses, the safety set will be used. All listings and tables will be presented by treatment group.

Safety summaries (tables, figures) include only data from the on-treatment period with the exception of baseline data which will also be summarized where appropriate (e.g. change from baseline summaries). In addition, a separate summary for death including on treatment and post treatment deaths will be provided. In particular, summary tables for adverse events (AEs) will summarize only on-treatment events, with a start date during the on-treatment period (treatment-emergent AEs).

The on-treatment period lasts from the date of first administration of study treatment to 90 days (EOS) after the date of actual administration of any study treatment.

Adverse events

All information obtained on adverse events will be displayed by treatment group and participant.

The number (and percentage) of participants with treatment emergent adverse events (events started after the first dose of study medication or events present prior to start of blinded treatment but increased in severity based on preferred term) will be summarized in the following ways:

- by treatment, primary system organ class and preferred term.
- by treatment, primary system organ class, preferred term and maximum severity.

Separate summaries will be provided for study medication related adverse events, death, serious adverse events, and other significant adverse events leading to discontinuation.

The number (and proportion) of participants with adverse events of special interest will be summarized by treatment group.

A participant with multiple adverse events within a primary system organ class is only counted once towards the total of the primary system organ class.

Vital signs

All vital signs data will be summarized by treatment group and visit/time and if ranges are available, abnormalities (and relevant orthostatic changes) will be flagged. Summary statistics will be provided by treatment group and visit/time for raw and change from baseline.

12-lead ECG

PR, QRS, QT, QTcF, and RR intervals will be obtained from 12-lead ECGs for each participant during the study. **CCI**

Categorical analysis of QT/QTc interval data based on the number of participants meeting or exceeding predefined limits in terms of absolute QT/QTc intervals or changes from baseline will be presented. In addition, a listing of these participants will be produced by treatment group.

All ECG data will be listed by treatment group, participant, and visit/time; abnormalities will be flagged. All ECG data will be summarized by treatment group and visit/time.

Clinical laboratory evaluations

All laboratory data will be summarized by treatment group, and visit/time.

All laboratory data parameters (hematology, biochemistry and Urinalysis) will be listed by treatment group, participant, and visit/time and if normal ranges are available abnormalities will be flagged.

9.4.2 Acute Kidney Injury Network (AKIN) criteria

Proportion of patients developing AKI as defined by the AKIN (Acute Kidney Injury Network) criteria within 7 days post dose using SCr will be summarized by treatment groups and listed by visit, participant and by treatment group.

9.4.3 Immunogenicity

Immunogenicity results will be listed by treatment group, participant and visit/time. The listing will contain ADA status (negative or positive) and for ADA-positive samples a titer and CCI. Participants with one or more treatment emergent ADAs are counted as ADA-positive participants and they will be summarized by treatment group to derive an ADA incidence. CCI

Visualizations overlaying ADA status including characterizations, CCI and potentially efficacy read-outs, may be presented.

9.4.4 Acute Kidney Disease (AKD)

MAKE30 is defined as the proportion of patients developing at least one of the following:

1. death through day 30,
2. initiation for renal replacement therapy through day 30, or
3. $\geq 25\%$ reduction in eGFR from baseline to 30 days after surgery.

MAKE90 is defined as the proportion of patients developing at least one of the following:

1. death through day 90,
2. initiation for renal replacement therapy through day 90, or
3. $\geq 25\%$ reduction in eGFR from baseline to 90 days after surgery.

Proportion of patients developing the MAKE90 will be summarized by treatment and listened by participant and treatment.

Proportion of patients developing the MAKE30 will be summarized by treatment and listened by participant and treatment.

Similarly, the proportion of patients with occurrence of individual components of MAKE90 and MAKE30 mentioned above will be summarized by treatment and listed by participant and treatment.

9.5 Exploratory endpoint(s)/estimand(s) analysis

9.5.1 CCI

CCI

[REDACTED]

[REDACTED]

[REDACTED]

9.5.2 CCI

CCI

[REDACTED]

[REDACTED]

9.5.3 CCI

CCI

[REDACTED]

[REDACTED]

[REDACTED]

Summary statistics will include mean (arithmetic and geometric), standard deviation (SD), CV

CCI

Table 9-1

CCI

CCI

9.6 (Other) Safety analyses

Not applicable.

9.7 Other analyses

Other exploratory endpoints will be presented as appropriately. More details will be provided in the study Statistical Analysis Plan.

9.8 Interim analysis

CCI

9.9 Sample size determination

9.9.1 Primary endpoint(s)

CCI

10 Supporting documentation and operational considerations

10.1 Appendix 1: Regulatory, ethical, and study oversight considerations

10.1.1 Regulatory and ethical considerations

This study will be conducted in accordance with the protocol and with the following:

- Consensus ethical principles derived from international guidelines including the Declaration of Helsinki and Council for International Organizations of Medical Sciences (CIOMS) international ethical guidelines
- Applicable ICH Good Clinical Practice (GCP) guidelines
- Applicable laws and regulations

The protocol, protocol amendments, ICF, Investigator's Brochure, [IDFU], and other relevant documents (e.g., advertisements) must be submitted to an IRB/IEC by the Investigator and reviewed and approved by the IRB/IEC before the study is initiated.

Any amendments to the protocol will require IRB/IEC approval before implementation of changes made to the study design, except for changes necessary to eliminate an immediate hazard to study participants.

Protocols and any substantial amendments/modifications to the protocol will require health authority approval prior to initiation except for changes necessary to eliminate an immediate hazard to study participants.

The Investigator will be responsible for the following:

Signing a protocol signature page confirming his/her agreement to conduct the study in accordance with these documents and all of the instructions and procedures found in this protocol and to give access to all relevant data and records to Novartis monitors, auditors, Novartis Quality Assurance representatives, designated agents of Novartis, IRBs/IECs, and regulatory authorities as required

Providing written summaries of the status of the study to the IRB/IEC annually or more frequently in accordance with the requirements, policies, and procedures established by the IRB/IEC

Notifying the IRB/IEC of SAEs or other significant safety findings as required by IRB/IEC procedures

Providing oversight of the conduct of the study at the site and adherence to requirements of 21 CFR, ICH guidelines, the IRB/IEC, European regulation 536/2014 for clinical studies (if applicable), European Medical Device Regulation 2017/745 for clinical device research (if applicable), and all other applicable local regulations

Inform Novartis immediately if an inspection of the clinical site is requested by a regulatory authority

This clinical study was designed and shall be implemented, executed and reported in accordance with the ICH Harmonized Tripartite Guidelines for Good Clinical Practice, with applicable local regulations (including European Directive 2001/20/EC or European Clinical Trial Regulation 536/2014, US CFR 21), and with the ethical principles laid down in the Declaration of Helsinki.

